6.2.1. Management of Hypertension

Hypertension (HTN) that occurs during study treatment must be treated with anti-hypertensive drugs prior to any dose reduction. Recommended management of HTN for subjects receiving study drug is presented in Appendix C.

Persistent HTN is defined as 2 consecutive elevated blood pressure (BP) measurements preferably taken in the clinic and obtained at least 1 hour apart. It is recommended that 24-48 hours should elapse between the decision steps. For a listing of recommended DHP (dihydropyridine) calcium channel blockers, angiotensin converting enzyme (ACE) inhibitors, and angiotensin receptor blockers, see Appendix C, Recommended Antihypertensive Medications. Note: If a subject has controlled HTN on an anti-hypertensive regimen at baseline and then develops a worsening of HTN requiring more intensive therapy then the previous regimen, this would be considered Grade 3 HTN.

6.3 Anticipated Toxicities of Enzalutamide

A comprehensive list of adverse events associated with enzalutamide can be found in the package insert for this product. This is generally a well tolerated agent, and in the placebocontrolled phase 3 trial in mCRPC, a similar number of AEs were observed in the enz-treated patients and in the placebo-treated patients. The most common adverse events were fatigue (34%), diarrhea (21%), hot flashes (20%), pain (14%) and headache (12%). Cardiac disorders and liver function abnormalities occurred at similar percentages in the enz-treated and placebotreated patients. Seizures occurred in 5 patients in the enzalutamide group, and 0 patients in the placebo group.

6.4 Enzalutamide Dose Modification

Dose modification of enzalutamide will generally not be permitted. Patients who experience Grade 3 or greater toxicity related to enzalutamide that cannot be ameliorated by the use of adequate medical intervention should have treatment interrupted until the toxicity improves to Grade 2 or lower severity. A treatment break of up to 4 weeks is permitted. If a patient experiences unacceptable toxicity related to enzalutamide at 160 mg/day, he should be removed from study unless specific permission to restart at a reduced dose is granted by the PI.

Dose escalation of enzalutamide above 160 mg/day will not be allowed.

7. DRUG FORMULATION AND ADMINISTRATION

7.1 Tivozanib

7.1.1 Description

Tivozanib is a small molecule inhibitor of receptor tyrosine kinases, and has the chemical name (N-{2-Chloro-4-[(6,7-dimethoxy-4-quinolyl)oxy]phenyl}-N'-(5-methyl-3-isoxazolyl)urea hydrochloride monohydrate.

7.1.2 Form

Tivozanib hydrochloride is formulated for oral administration as a dark blue/bright yellow or bright yellow number 4 gelatin capsule depending on the capsule strength (see below). The following dosage strengths will be made available:

- 1.5 mg (bright yellow capsule)
- 1.0 mg (dark blue/bright yellow capsule)

The amount of study drug dispensed to the subject at the beginning of every 3rd dosing cycle will be sufficient to allow for a total of 9 weeks (63 days) during which tivozanib hydrochloride will be taken orally once daily for 3 out of 4 weeks. Dosing compliance will be monitored at each clinic visit.

7.1.3 Storage and Stability

Tivozanib hydrochloride drug product should be stored at room temperature (15°–25°C) in a controlled access room that can be entered only by authorized pharmacy or investigative personnel.

Long-term stability studies conducted according to ICH guidelines support an expiration dating of 36 months for dose strengths ranging from 0.5 mg to 2.0 mg when stored at 15-25°C with allowable excursions up to 30°C. Tivozanib hydrochloride drug product is an investigational new drug. Accordingly, all drug handling and disposal procedures for orally administered investigational drugs should be performed by qualified personnel as documented by the American Hospital Formulary Service or other recognized formulary requirements.

Complete study drug information (including packaging, labeling, storage and disposition) is provided in the Tivozanib Hydrochloride Investigator's Brochure.

7.1.4 Availability

Tivozanib is an investigational product and will be supplied free-of-charge by the manufacturer.

7.1.5 Administration

Tivozanib should be taken at approximately the same time every day, preferably in the morning, with up to 200 mL of water. Tivozanib should be taken at least 1 hour before or 2 hours after ingesting any food or other medications. On days of a scheduled clinic visit, the dose of tivozanib should not be taken until after visit procedures are completed. If a dose is vomited or missed the dose should not be made up. Only one tivozanib capsule should be taken each day.

7.1.6 Accountability

Patients will be asked to keep a drug diary to document their daily dosing. Study drug accountability will be performed at scheduled study visits to document compliance. Any remaining capsules should be returned at the scheduled study visits.

The investigator, or a responsible party designated by the investigator, must maintain a careful record of the inventory and disposition of the agent (investigational or free of charge) using the NCI Drug Accountability Record or another comparable drug accountability form. (See the CTEP website at http://ctep.cancer.gov/protocolDevelopment for the "Policy and Guidelines for Accountability and Storage of Investigational Agents" or to obtain a copy of the drug accountability form.)

7.1.7 Destruction and Return

At the end of the study, unused supplies of tivozanib should be destroyed according to institutional policies. Destruction will be documented in the Drug Accountability Record Form.

7.2 Enzalutamide

7.2.1 Description

Enzalutamide has the chemical name 3-(4-cyano-3-trifluoromethylphenyl)-1-[3-fluoro-4 (methylcarbamoyl)phenyl]-5,5-dimethyl-2-thioxoimidazolin-4-one. The drug substance has no chiral centers and no salt forms are available at \sim pH 2 to 10. It is essentially insoluble in water, but partially soluble in lipid-based solutions.

7.2.2 Form

Enzalutamide will be supplied in 160 mg tablets. It is manufactured and supplied by Astellas (Chicago, IL) and Medivation (San Francisco, CA).

7.2.3 Storage and Stability

Study drug should be stored in a secure location with limited access within the following temperature range: 59°F to 86°F (15°C to 30°C). Bottles should be labeled with the study protocol number, medication or kit number, contents, directions for use, expiration date, and storage directions. Patients will be instructed to store study drug at room temperature out of the reach of children. The drug substance is formulated in the surfactant Labrasol to create a self-emulsifying (or microemulsifying) dosage form. The product will be provided as gelatin capsules in bottles with child-resistant caps.

7.2.4 Availability

Enzalutamide is a commercially available product, and is indicated for the treatment of men with mCRPC following failure of chemotherapy. For the purposes of this study, the product will be billed to patients' insurance.

7.2.5 Administration

Study drug doses should be taken at approximately the same time each day. If dosing is missed on one day for any reason, including vomiting of the dose, the dose should not be repeated or made up. On days of a scheduled clinic visit, the dose of enzalutamide should not be taken until after visit procedures are completed. Enzalutamide can be taken without regard to other food or beverage intake, and may be taken before or after tivozanib.

7.2.6 Accountability

Patients will be asked to keep a drug diary to document their daily dosing. Study drug accountability will be performed at scheduled study visits to document compliance. Any remaining capsules should be returned at the scheduled study visits.

The investigator, or a responsible party designated by the investigator, must maintain a careful record of the inventory and disposition of the agent (investigational or free of charge) using the NCI Drug Accountability Record or another comparable drug accountability form. (See the CTEP website at http://ctep.cancer.gov/protocolDevelopment for the "Policy and Guidelines for Accountability and Storage of Investigational Agents" or to obtain a copy of the drug accountability form.)

7.2.7 Destruction and Return

At the end of the study, unused supplies of enzalutamide should be destroyed according to institutional policies. Destruction will be documented in the Drug Accountability Record Form.

8. STUDY CALENDAR

Baseline evaluations are to be conducted within 3 weeks prior to start of protocol therapy. Subsequent evaluations should be carried out on Day 1 of subsequent cycles (+/- 3 days) every 12 weeks from Cycle 46 on. Radiographic evaluations including bone and abdominal/pelvic CT scans should be conducted at baseline and every 24 weeks from Cycle 46 on.

| | Pre- Study | Cycle 1 Day 1 ^x | Cycle 2 to Cycle 45, Day 1 ^x | Day 1 Cycles ≥ 46, Every 12 Weeks ^x | Off Study ^b |
|---|---------------|-------------------------------|---|--|------------------------|
| Treatment Schedule: | | | | | |
| Tivozanib | | X (days 1-21) | X (days 1-21) | X (days 1-21) | |
| Enzalutamide | | X (Days 1-28) | X (days 1-28) | X (days 1-28) | |
| Informed consent | X | | | | |
| Demographics | X | | | | |
| Medical/Interval history | X | X | X | X | X |
| Concurrent meds | X | X | X | X | X |
| Physical exam | X | X | X | X | X |
| Vital signs/ BP | X | X | X | X | X |
| Performance status | X | X | X | X | X |
| Serum PSA | X | | X | X | X |
| PT, PT/INR, and PTT | X | | | | |
| CBC w/diff, plts | X | X | X | X | X |
| Serum chemistry ^a | X | X | X | X | X |
| Serum testosterone | X | | | | |
| Thyroid Function (TSH only) | X | | X (odd cycles) | X | |
| Urinalysis (urine protein only) | X | X | X | X | X |
| Chest xray | X | | as clinicall | y indicated | |
| Bone scan and abdominal/pelvis CT scans | X | Rep | Repeat scans every 24 weeks | | X ^c |
| EKG | X | | | | |
| Adverse Event Evaluation | X | Х | | | -X |
| Survival follow-up | | | | | X ^d |

x: ± 3 days for treatment or assessment requirement

MEASUREMENT OF EFFECT

a: Sodium, potassium, chloride, BUN, creatinine, glucose, albumin, total protein, total bilirubin, alkaline phosphatase, SGOT [AST], SGPT [ALT]

b: Off-study evaluation should occur within 30 days after the last dose of study treatment c: Post-treatment scans will be performed if an assessment has not been performed within the prior 6 weeks

d: Follow for survival information every 3 months until death, up to 2 years after discontinuing therapy, or patient lost to follow-up

The primary endpoint of the study is progression free survival (PFS). Secondary clinical endpoints will include safety, overall survival, time to PSA progression, PSA response rate and objective response rate.

The consensus guidelines of RECIST 1.1 and PCWG2 have been taken into consideration for the determination of radiographic disease progression {Eisenhauer, 2009 #274;Scher, 2008 #261}. Disease progression will consist of confirmed radiographic disease progression, death due to disease, or clinical disease progression. Radiographic disease progression is defined either by RECIST 1.1 for soft tissue disease, or by the appearance of two or more new bone lesions on bone scan (PCWG2).

Confirmation of progression by RECIST requires redemonstration of soft tissue progression by a scan of the same modality a minimum of 4 weeks later.

If the initial restaging bone scan showed progression by PCWG2 (two or more bone lesions), then confirmation of progression by PCWG2 on the next bone scan requires two or more new bone lesions compared to the first bone scan showing progression. Additionally, at least two of the new lesions from the first scan must still be present.

If progression by PCWG2 occurs not on the initial bone scan but on subsequent bone scans, then confirmation of progression requires either persistence or increase in number of lesions compared to the first bone scan showing progression.

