5.1.3 Off Study Visit

The following data should be collected during the off study visit:

- History and physical exam
- Concomitant medications
- Vital signs (including blood pressure, body temperature, heart rate and respiratory rate)
- ECOG performance status
- Serum PSA
- Complete blood count
- Serum chemistries
- Urinalysis (protein only)
- Bone scan and abdominal/pelvic CT scans (performed if an assessment has not been performed within the prior 6 weeks)
- Adverse event assessments

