5.6 Criteria for Removal from Study

Participants will be removed from study when any of the criteria listed in Section 5.4 applies. The reason for study removal and the date the participant is removed must be documented in the study-specific case report form (CRF). Alternative care options will be discussed with the participant.

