9.1.3 Response Criteria

9.1.3.1 Evaluation of Target Lesions

Complete Response (CR): Disappearance of all target lesions. Any pathological lymph node must have reduction in short axis to < 10 mm.

Partial Response (PR): At least a 30% decrease in the sum of the diameters of target lesions, taking as reference the baseline sum diameters.

Progressive Disease (PD): At least a 20% increase in the sum of the diameters of target lesions, taking as reference the smallest sum on study with at least a 5 mm absolute increase in the sum of all lesions. The appearance of one or more new lesions* denotes disease progression.

Stable Disease (SD): Neither sufficient shrinkage to qualify for PR nor sufficient increase to qualify for PD, taking as reference the smallest sum diameters while on study.

Unknown (UN): Assessment of target lesions cannot be made due to insufficient or unevaluable data.

*Definition of New Lesion: The finding of a new lesion should be unequivocal (i.e. not due to difference in scanning technique, imaging modality, or findings thought to represent something other than tumor (ex: new bone lesions may be healing or flare of pre-existing lesions). However, a lesion identified on a follow-up scan in an anatomical location that was not scanned at baseline is considered new and will indicate PD. If a new lesion is equivocal (because of small size, etc.), follow-up evaluation will clarify if it truly represents new disease and if PD is confirmed, progression should be declared using the date of the initial scan on which the lesion was discovered.

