9.1.4 Progression-Free Survival

Progression-Free Survival (PFS) is defined as the duration of time from registration to time of documented disease progression (radiographic or clinical) or death without documentation of disease progression. Patients who are alive and without evidence of progression will be censored at the date of last disease evaluation.

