14. STATISTICAL CONSIDERATIONS

14.1. Study Design/Endpoints

The phase 2 study will evaluate the efficacy of enzalutamide and tivozanib in patients with mCRPC. The primary endpoint will be progression free survival (PFS), defined as the time from registration to the earlier of progression (radiographic or clinical) or death and, if censored, the date of last disease evaluation. Based on phase 3 data, the median PFS with enzalutamide alone in chemotherapy naive mCRPC is 14 months. The hypothesis is that the addition of tivozanib will significantly enhance efficacy. An improvement of 60% to a median PFS of 22.4 months will be considered worthy of further study. Assuming exponential distribution, this implies a hazard ratio (HR) of 0.625 relative to historical control (hazard rate from 0.0495 to 0.0309). Using a one-sample exponential test, there will be 80% power to demonstrate a 60% improvement at a one-sided Type 1 error rate of 10% with enrollment of 38 patients and 20 PFS events.

Because this combination has not been previously tested, a safety run-in will be conducted at the outset of the trial. After the first 3 patients are enrolled, accrual will be held until all three patients complete the first 1 month of treatment. Additionally, after a total of 10 patients are enrolled, these patients will be analyzed for safety and toxicity by the DSMC. If any treatment-related, expected or unexpected grade 3 or higher adverse events occur during the first month of treatment in the first 3 patients, or if the rate is >30% among the first 10 patients during the first month of treatment, further accrual will be halted for reconsideration of the appropriateness of the dosing schedules.

The table below gives the probability of observing 1 or more toxicities among the first 3 patients or 3 or more among the first 10 patients given different true underlying toxicity rates.

| True toxicity rate | 1% | 10% | 20% | 30% | 40% | 50% |
|--|--------|-------|-------|-------|-------|-------|
| Probability of Stopping Early (≥ 1/3) | 0.030 | 0.271 | 0.488 | 0.657 | 0.784 | 0.875 |
| Probability of Stopping Early (≥ 3/10) | <0.001 | 0.070 | 0.322 | 0.617 | 0.832 | 0.945 |

Thus, if the true underlying proportion of toxic events is 30% at the current dosing schedules, there is a greater than 60% chance of stopping early.

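### The plan defines radiographic progression in two ways and gives no general event date, so PFS events can be lost or dated late and type I error can exceed 10%

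*Combined protocol and SAP*

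**What the plan says.** The opening text of Section 9 (Measurement of Effect, printed directly after the Section 8 calendar) defines the event: "Disease progression will consist of confirmed radiographic disease progression, death due to disease, or clinical disease progression". For soft tissue it adds: "Confirmation of progression by RECIST requires redemonstration of soft tissue progression by a scan of the same modality a minimum of 4 weeks later". Bone progression on the initial restaging scan needs two or more further new lesions on the next bone scan. Bone progression first seen later needs persistence or an increase, with no interval given. Section 5.1 schedules bone and CT scans every 3 cycles (12 weeks) up to Cycle 46.

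Section 9.1.4 defines PFS differently, as time to "documented disease progression (radiographic or clinical) or death without documentation of disease progression". It censors, at the last disease evaluation, men who are alive with no evidence of progression. Section 14.1 likewise says progression, radiographic or clinical, with no mention of confirmation.

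On leaving: Section 1.1 ends treatment at objective or clinical progression, Section 5.4 lists disease progression, and Section 5.6 says "Participants will be removed from study when any of the criteria listed in Section 5.4 applies". Off-study scans are "performed if an assessment has not been performed within the prior 6 weeks" (Section 5.1.3; Section 8, note c), and the off-study visit falls within 30 days of the last dose (Section 8, note b). Section 5.5 then follows survival only. Section 9.1 mentions confirmatory scans only for objective response.

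The one dating rule is in Section 9.1.3.1. It covers a new lesion that is at first equivocal: "progression should be declared using the date of the initial scan on which the lesion was discovered".

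**The concern.** A man with a first progression scan and no second scan is not a progression under the opening of Section 9, but is one under Sections 9.1.4 and 14.1. The conduct rules make such men likely. Six weeks is 42 days and the off-study visit is at most 30 days after the last dose, so anyone whose last dose falls within 42 − 30 = 12 days after the progression scan is inside the window in which no scan is required. For a man who is confirmed, the text does not say whether the event falls on the first or the confirming scan.

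The trial has a single arm tested against a fixed historical median, so no concurrent control has its PFS lengthened by the same rule. The test compares total progression-free time with the number of events. A lost event lowers the count, and a late date adds time. Both move the result towards declaring the combination active.

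**Working it through.** **Inputs from Sections 14.1 and 14.2.** Null median 14 months, alternative 22.4 months, hazard ratio 0.625, 20 events, 38 evaluable and 42 enrolled men, 21 months' accrual. The method is stated as "Using a one-sample exponential test", with "80% power to demonstrate a 60% improvement at a one-sided Type 1 error rate of 10" (per cent).

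**Assumed, because the documents do not give them.** Radiographic share of PFS events: 50%, 75% or 100%. Share of radiographic events lost: 10% or 20%. Delay from dating at confirmation: 4 weeks (soft-tissue minimum) or 12 weeks (next scheduled scan).

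**Step 1: reproduce the design.** λ0 = ln 2 / 14 = 0.0495 per month. With total progression-free time T at 20 events, reject if 2·λ0·T > χ²(0.90; 40 df) = 51.805. Size is 0.100. Power = P(χ²40 > 0.625 × 51.805 = 32.378) = 0.799, so the stated 80% reproduces. Success needs an estimated median of 14 × 51.805 / 40 = 18.1 months.

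**Step 2: lost events.** Suppose a fraction f of all events is censored at the progression time. Counted events then arrive at rate λ0(1 − f) per month of exposure, and size = P(χ²40 > 51.805 × (1 − f)), where f = radiographic share × share lost.

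| Radiographic share | 10% lost: f, threshold, size | 20% lost: f, threshold, size |
|---|---|---|
| 50% | 0.05, 49.215, 0.151 | 0.10, 46.625, 0.219 |
| 75% | 0.075, 47.920, 0.182 | 0.15, 44.034, 0.305 |
| 100% | 0.10, 46.625, 0.219 | 0.20, 41.444, 0.408 |

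**Step 3: late dating.** Four weeks is 28/30.44 = 0.92 month and 12 weeks is 84/30.44 = 2.76 months. A floor comes from adding the delay only to the 20 counted events, all taken as radiographic:

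- 4 weeks: 51.805 − 2 × 0.0495 × 20 × 0.92 = 49.98, size 0.134.
- 12 weeks: 51.805 − 2 × 0.0495 × 20 × 2.76 = 46.34, size 0.227.

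The true effect is larger, because men who have progressed but are not yet confirmed also add exposure. Simulation with a true median of 14 months, uniform accrual over 21 months and analysis at the 20th counted event (range over 38 and 42 men) gives:

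| Radiographic share | 4 weeks late | 12 weeks late |
|---|---|---|
| 50% | 0.13–0.14 | 0.22–0.23 |
| 75% | 0.15–0.16 | 0.30–0.34 |
| 100% | 0.17–0.18 | 0.41–0.46 |

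With no loss and no delay the simulation returns 0.10.

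**The case against.** The strongest reply is that the documents, read together, need not lose anyone.

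- **Leaving.** Section 9 defines disease progression as confirmed, and Sections 5.4 and 5.6 remove men at disease progression, so they may be meant to stay until confirmation. The reference to the next bone scan supports this. A reader might infer that men leave at the first, unconfirmed scan. That is one reading, suggested by the word objective in Section 1.1, but it is not stated.
- **Censoring.** A reader might also infer that the plan orders these men to be censored. It does not: Section 9.1.4 censors only men without evidence of progression, and its wording could count the first scan as an event.
- **Scans.** It would be too strong to say that no further scan is done. A man who leaves more than 6 weeks after his last scan is due one.
- **Other events.** Clinical progression and death count without confirmation, so deterioration judged to be clinical progression is not lost. The routes to loss are mainly toxicity, withdrawal or new therapy between the two scans.
- **Benchmark.** If the historical 14 months rests on a matching confirmation and dating rule, part of the bias cancels.

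All five stand, and they limit the size of the problem. They do not remove it. If men stay until confirmation, the event date is still open, and a man who leaves in between still has no agreed status. If men leave at the first scan, the confirmation that Section 9 requires is normally missing.

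**Conclusion.** The point holds as a contradiction in the primary endpoint plus a missing dating rule. It does not hold as a stated rule that censors progressions. Applied literally, the Section 9 wording can raise type I error from 10% to between about 13% (half of events radiographic, 4 weeks late) and about 46% (all radiographic, all 12 weeks late). The upper end needs every event to be radiographic and every confirmation to wait for the next scheduled scan, so it is a bound and not a forecast.

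The direction is certain only relative to a benchmark dated at first documentation. The documents give neither the share of events affected nor the rule behind the historical median. It would therefore be wrong to conclude that type I error does rise; it can, and in each scenario above it exceeds the nominal level.

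**What to change.** In Sections 9, 9.1.4 and 14.1, state one rule for the PFS analysis:

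1. Confirmed radiographic progression is dated at the first scan that showed it.
2. Radiographic progression with no later scan is a PFS event on the date of that first scan.
3. Only a progression that a later scan fails to confirm under the Section 9 criteria is set aside.

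Add a sensitivity analysis that counts every first-documented progression. If the plan's sources allow it, state how progression was confirmed and dated for the 14-month figure.

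Separately, the sponsor must reconcile Sections 1.1, 5.4 and 5.6 with Section 9 on whether first or confirmed progression is meant. No clinical rule is proposed here.

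The cost is a few sentences, settled before the PFS analysis. No scans are added and no treatment rule changes. A few unconfirmed bone flares may count as events, which is the conservative direction. With no progression lost or dated late, the design keeps its 0.100 size and 0.799 power at 20 events.
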